11.0 Treatment Evaluation

11.1 Response Considerations

Definitions for clinical response for patients with lymphoma are from the Cheson et al. Revised Response Criteria for Malignant Lymphoma .(28) Lymph node measurements should be taken from the CT portion of the PET/CT, or MRI scans, or dedicated CT scans where applicable. Measurement of lymphadenopathy will be determined by adding the sum of the products of the maximal perpendicular diameters of measured lesions (SPD). Measurable extranodal disease should be assessed in a manner similar to that for nodal disease. For these recommendations, the spleen is considered nodal disease. Disease that is only assessable (eg, pleural effusions, bone lesions) will be recorded as present or absent only, unless, while an abnormality is still noted by imaging studies or physical examination, it is found to be histologically and pathologically negative

Response is based on CT alone or the CT component of PET/CT or MRI where applicable.

Response criteria, modified from Cheson et al. 2007.

Response Category	Definition	Nodal Masses	Spleen, liver	Bone Marrow
CR	Disappearance of all evidence of disease.	Regression to normal size on CT	Not palpable, nodules disappeared	Infiltrate cleared on repeat biopsy; if indeterminate by morphology, immunohistochemistry should be negative
PR	Regression of measurable disease and no new sites	≥50% decrease in SPD of up to 6 largest dominant masses; no increase in size of other nodes and regression on CT	≥50% decrease in SPD of nodules (for single nodule in greatest transverse diameter); no increase in size of liver or spleen	Irrelevant if positive prior to therapy; cell type should be specified
SD	Failure to attain CR/PR or PD	No change in size of previous lesions on CT		
PD (Relapse/Progressive disease)	Any new lesion or increase by ≥50% of previously involved sites from nadir	Appearance of a new lesion(s) > 1.5 cm in any axis, ≥50% increase from nadir in SPD of more than one node, or ≥50% increase in longest diameter of a previously identified node > 1 cm in short axis.	> 50% increase from nadir in the SPD of any previous lesions	New or recurrent involvement

Abbreviations: CR, complete response; FDG, [¹⁸F]fluorodeoxyglucose; PET, positron emission tomography; CT, computed tomography; PR, partial response; SPD, sum of the product of the diameters; SD, stable disease; PD, progressive disease.

11.11 **Complete Response (CR).** The designation of CR requires all of the following:

- 11.111 Complete disappearance of all detectable clinical evidence of disease and definitely disease-related symptoms if present before therapy.
- 11.112 All lymph nodes and nodal masses must have regressed on CT to normal size (≤ 1.5 cm in their greatest transverse diameter for nodes > 1.5 cm before therapy). Previously involved nodes that were 1.1 to 1.5 cm in their long axis and more than 1.0 cm in their short axis before treatment must have decreased to ≤ 1.0 cm in their short axis after treatment. .
- 11.113 The spleen and/or liver, if considered enlarged before therapy on the basis of a physical examination or CT scan, should not be palpable on physical examination and should be considered normal size by imaging studies, and nodules related to lymphoma should disappear. However, determination of splenic involvement is not always reliable because a spleen considered normal in size may still contain lymphoma, whereas an enlarged spleen may reflect variations in anatomy, blood volume, the use of hematopoietic growth factors, or causes other than lymphoma. Similarly, other organs considered to be enlarged before therapy due to involvement by lymphoma, such as liver and kidneys, must have decreased in size.
- 11.114 If the bone marrow was involved by lymphoma before treatment, the infiltrate must have cleared on repeat bone marrow biopsy. The biopsy sample on which this determination is made must be adequate (with a goal of > 20 mm unilateral core). If the sample is indeterminate by morphology, it should be negative by immunohistochemistry. A sample that is negative by immunohistochemistry but that demonstrates a small population of clonal lymphocytes by flow cytometry will be considered a CR until data become available demonstrating a clear difference in patient outcome.

11.12 **Criteria for Partial Response (PR).** The designation of PR requires all of the following:

- 11.121 At least a 50% decrease in sum of the product of the diameters (SPD) of up to six of the largest dominant nodes or nodal masses. These nodes or masses should be selected according to all of the following:
 - they should be clearly measurable in at least 2 perpendicular dimensions
 - if possible they should be from disparate regions of the body
 - they should include mediastinal and retroperitoneal areas of disease whenever these sites are involved
- 11.122 No increase should be observed in the size of other nodes, liver, or spleen.

- 11.123 Splenic and hepatic nodules must regress by $\geq 50\%$ in their SPD or, for single nodules, in the greatest transverse diameter.
- 11.124 With the exception of splenic and hepatic nodules, involvement of other organs is usually assessable and no measurable disease should be present.
- 11.125 Bone marrow assessment is irrelevant for determination of a PR if the sample was positive before treatment. However, if positive, the cell type should be specified (eg, large-cell lymphoma or small neoplastic B cells). Patients who achieve a CR by the above criteria, but who have persistent morphologic bone marrow involvement will be considered partial responders.
When the bone marrow was involved before therapy and a clinical CR was achieved, but with no bone marrow assessment after treatment, patients should be considered partial responders.
- 11.126 No new sites of disease should be observed.
- 11.127 CT criteria should be used

11.13 **Criteria for Stable Disease (SD)**

- 11.131 A patient is considered to have SD when he or she fails to attain the criteria needed for a CR or PR (see above), but does not fulfill those for progressive disease (see below).
- 11.132 There must be no change in the size of the previous lesions on the post-treatment CT scan.

11.14 **Relapsed Disease (after CR)/Progressive Disease (PD) (after PR, SD):**
Lymph nodes should be considered abnormal if the long axis is more than 1.5 cm regardless of the short axis. If a lymph node has a long axis of 1.1 to 1.5 cm, it should only be considered abnormal if its short axis is more than 1.0. Lymph nodes $\leq 1.0 \times \leq 1.0$ cm will not be considered as abnormal for relapse or progressive disease.

- 11.141 Appearance of any new lesion more than 1.5 cm in any axis during or at the end of therapy, even if other lesions are decreasing in size. Increased FDG uptake in a previously unaffected site should only be considered relapsed or progressive disease after confirmation with other modalities. In patients with no prior history of pulmonary lymphoma, new lung nodules identified by CT are mostly benign. Thus, a therapeutic decision should not be made solely on the basis of the PET without histologic confirmation.

11.142 At least a 50% increase from nadir in the SPD of any previously involved nodes, or in a single involved node, or the size of other lesions (eg, splenic or hepatic nodules). To be considered progressive disease, a lymph node with a diameter of the short axis of less than 1.0 cm must increase by $\geq 50\%$ and to a size of 1.5 x 1.5 cm or more than 1.5 cm in the long axis.

11.143 At least a 50% increase in the longest diameter of any single previously identified node more than 1 cm in its short axis.

12.0 Descriptive Factors

12.1 Follicular Lymphoma International Prognostic Index 2 (FLIPI2) (29) low risk (0 risk factors) vs. intermediate risk (1 or 2 risk factors) vs. high risk (3-5 risk factors)

Risk Factors	0 points	1 point
$\beta 2$ -microglobulin	\leq ULN	$>$ ULN
Longest diameter of the largest involved node	\leq 6 cm	$>$ 6 cm
Bone marrow involvement	No	Yes
Hemoglobin Level	≥ 12 g/dL	< 12 g/dL
Age	≤ 60 years	> 60 years

Total number of risk factors = sum of the number of points for each prognostic factor

13.0 Treatment/Follow-up Decision at Evaluation of Patient

13.1 Patients will be evaluated per the test schedule during cycle 1 of treatment.

13.2 After treatment, patients will be observed at 3, 6, 9, 12, 18, 24, 30, 36, 48, and 60 months from day 1 of treatment.

13.3 Criteria for removing patients from treatment and initiating observation.

13.3.1 Requested withdrawal or patient non-compliance.

13.4 Patients who have progressive or relapsed disease, receive subsequent treatment for lymphoma, refuse further observation, or fail to return for evaluation during observation will go to event monitoring.

13.5 At 5 years from day 1 of treatment, all patients still on observation will go to event monitoring every 12 months until 10 years from time of registration per Section 18.0.

13.6 A patient is deemed *ineligible* if after registration, it is determined that at the time of registration, the patient did not satisfy each and every eligibility criteria for study entry.

The patient may continue protocol treatment at the discretion of the physician as long as there are no safety concerns, and the patient was properly registered. The patient will continue treatment (if no safety concerns), observation, and event monitoring as specified for all patients (or will be taken off study, if applicable).

- If the patient received treatment, the patient will continue treatment (if no safety concerns), observation, and event monitoring as specified for all patients.
- If the patient never received treatment, On-study material and the End of Active Treatment/Cancel Notification Form must be submitted. No further data submission is necessary.

13.7 A patient is deemed a *major violation*, if protocol requirements regarding treatment in cycle 1 of the initial therapy are severely violated that evaluability for primary end point is questionable. The patient may continue protocol treatment at the discretion of the physician as long as there are no safety concerns, and the patient was properly registered. The patient will continue treatment (if no safety concerns), observation, and event monitoring as specified for all patients.

13.8 A patient is deemed a *cancel* if he/she is removed from the study for any reason before any study treatment is given. On-study material and the End of Active Treatment/Cancel Notification Form must be submitted. No further data submission is necessary.

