16.0 Statistical Considerations and Methodology

16.1 Overview: This is a randomized phase III study designed to compare the complete response rate at 6 months between Rituximab (Arm A) and Zevalin (Arm B) for treatment of asymptomatic follicular lymphoma.

16.11 Primary Endpoint: The primary endpoint of this study is the complete response rate at the 6-month disease assessment which will be compared between the two arms. A patient is considered to be a complete responder if the objective status at the 6-month disease assessment is a complete response. Any patient not meeting the definition of a complete response will be considered as a non-responder for the primary endpoint. A modified intent-to-treat approach will be employed for the primary analysis such that all randomized subjects meeting the eligibility criteria who do not cancel participation prior to treatment initiation and did not experience a major treatment violation (during the first cycle of treatment) will be included in the primary analysis. Sensitivity analysis will be conducted including all patients who did not cancel participation prior to

treatment initiation. The percentage of patients in each response category (e.g., CR, PR, STAB, Relapse/PD) will also be tabulated by arm.

16.2 Statistical Considerations:

16.21 Statistical Design:

Previous studies of treatment with four doses of single agent Rituximab in this patient population have shown CR rates of 6-33% (9 and 10). In addition, preliminary results of an additional study, the RESORT ECOG trial, show a CR rate of 15% in this same population (11). This study is designed to detect an improvement in complete response rate from 20% with Rituximab (Arm A) to 50% with Zevalin (Arm B). The proportion of patients who have a CR at 6 months will be evaluated and compared between the two treatment regimens using a two-sided $\alpha=0.05$ continuity corrected Cochran–Mantel–Haenszel (CMH) test with stratification factors as defined in Section 5.0.

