The primary goal of this trial is to compare the CR rate at 6 months between Rituximab and Zevalin. We will randomize 116 evaluable patients in a 1:1 ratio to Rituximab or Zevalin. This final analysis will take place after all patients have completed the disease assessment at 6 months. A sample size of 58 evaluable patients per arm (116 total evaluable) provides 90% power to detect an improvement in complete response rate from 20% to 50%, using a two-sided chi-square test at a significance level of 0.05. To ensure that 116 evaluable patients are randomized, we will enroll/randomize **128 total patients**.

The CR rate in each arm will be estimated by the number of evaluable patients who achieve a CR as the objective status on the disease assessment at 6 months divided by the total number of randomized evaluable patients in that arm. The CR rates will be compared between the two arms. If the CR rate is higher in the Zevalin arm, where the p-value is less than 0.05, this will be considered sufficient evidence that the Zevalin arm may be recommended for further testing in subsequent studies.

This study will use a dynamic allocation procedure to allocate an equal number of patients to each of the two treatment regimens.(30) This procedure will balance the marginal distributions of the stratification factors between these two treatment arms. The stratification factors that will be used are listed in Section 5.0.

This study will be based on a modified intent-to-treat approach including all randomized patients meeting the eligibility criteria who do not cancel participation prior to treatment initiation and did not experience a major treatment violation (during the first cycle of treatment) based on the randomized treatment assignment.

The study will be permitted to be published after all patients have undergone the 6-month disease assessment to establish the CR rate between each arm. This essentially fulfills the first goal of the study. See Section 16.3 for further analysis plans.

16.23 Other considerations: Adverse events, quality/duration of response, and patterns of treatment failure observed in this study, as well as scientific discoveries or changes in standard care will be taken into account in any decision to terminate the study.

16.24 Sample Size: This study is expected to accrue a maximum of 128 patients unless undue toxicity is encountered.

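### The primary CR comparison drops treated, randomised patients under a loosely defined major-violation label that can be applied after the month-6 response is known

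*Combined protocol and SAP*

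**What the plan says.** Section 16.11 limits the primary analysis to randomised, eligible patients who started treatment and who "did not experience a major treatment violation (during the first cycle of treatment) will be included in the primary analysis". Section 16.21 repeats the restriction: "did not experience a major treatment violation (during the first cycle of treatment) based on the randomized treatment assignment".

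Section 13.7 is the only place that defines a major violation: "protocol requirements regarding treatment in cycle 1 of the initial therapy are severely violated that evaluability for primary end point is questionable". It adds: "The patient will continue treatment (if no safety concerns), observation, and event monitoring as specified for all patients".

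Two other provisions cover the same kind of patient:

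- Section 13.3.1 gives the reason for leaving treatment and starting observation: "Requested withdrawal or patient non-compliance".
- Section 16.11 settles the endpoint for anyone without a CR: "Any patient not meeting the definition of a complete response will be considered as a non-responder for the primary endpoint".

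Section 16.11 also plans a wider analysis: "Sensitivity analysis will be conducted including all patients who did not cancel participation prior to" treatment initiation. The decision rule in 16.21 rests on the primary comparison: "If the CR rate is higher in the Zevalin arm, where the p-value is less than 0.05, this will be considered sufficient evidence" to recommend Zevalin for further testing.

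**The concern.** Missing or stopping assigned treatment happens after randomisation and can be a consequence of that treatment. Removing such patients when they are not in CR raises the CR rate of their arm. In Arm B this favours Zevalin; in Arm A it works against it. The documents do not show which arm would lose more.

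The label is a judgement about severity and evaluability. No infusion or dose threshold, adjudicator or masking is given. The cycle-1 limit fixes when the violation occurs, not when it is classified.

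The definition also turns on whether the primary endpoint can be evaluated. Section 16.11 already makes every analysed patient evaluable, because anyone without a CR is a non-responder. A patient who withdraws or does not comply under 13.3.1 therefore appears to stay in as a non-responder, yet nothing prevents the same patient being labelled a violation and removed. At stake is whether the set behind the p<0.05 decision is fixed independently of the outcome.

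**Working it through.** **Inputs from the plan.** CR 20% (Arm A) vs 50% (Arm B), two-sided 0.05, 90% power, 58 evaluable per arm, 128 randomised 1:1, continuity-corrected CMH test (16.21). Cycle-1 dosing is on days 1, 8, 15 and 22 in Arm A and days 1 and 8 in Arm B (7.1, 7.2).

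**The plan's own figure.** With p̄ = 0.35 and difference 0.30, the uncorrected size is

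n = [1.960·√(2·0.35·0.65) + 1.282·√(0.2·0.8 + 0.5·0.5)]² / 0.30² = 51.0, so 52 per arm.

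The continuity correction gives (51.0/4)·[1 + √(1 + 4/(51.0·0.30))]² = 57.5, so 58 per arm. The stated size reproduces. Exact power of the unstratified corrected test at 58 per arm is 90.6%. The allowance for non-evaluable patients is 128 − 116 = 12, shared by cancels, ineligibles and violations.

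**Assumptions.** The plan gives no number or arm split of violations. Let kA and kB treated patients stop early, none in CR; the other patients respond at the design rates. The decision is that Zevalin's CR rate is higher and the continuity-corrected chi-square has p<0.05:

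X² = N(|ad − bc| − N/2)² / (product of the four margins).

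Every binomial outcome is enumerated twice, with stoppers excluded and with stoppers counted as non-responders. The tabulated quantity is the probability that the two decisions differ.

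| Stoppers | 64 per arm | 61 per arm* |
|---|---|---|
| 1 in each arm | 0.03% | 0.0% |
| 3 in each arm | 0.3% | 0.5% |
| 6 in each arm | 1.1% | not shown |
| 2, 4, 6 all in B | 2.5%, 4.9%, 7.7% | 2.6%, 6.3%, 11.0% |
| 2, 4, 6 all in A | 1.7%, 3.0%, 4.5% | not shown |

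*If cancels and ineligibles already use 6 of the 12; 6 in each arm would then exceed the allowance.

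**If stoppers can respond.** Suppose they reach CR at half their arm's rate (10% in A, 25% in B; 64 per arm). Four in B changes the decision in 2.6% of trials if all are labelled and 3.1% if only those without CR are. Three in each arm gives 2.0% and 0.6%.

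**Stratified check.** This used 12,000 simulations of the corrected CMH test over 8 strata, with assumed shares of 50%, 30% and 15% for one level of each factor and no minimisation. With 64 per arm it gives 0.6% (1 in each arm), 1.1% (3 in each arm) and 2.2%, 5.5%, 9.3% (2, 4, 6 all in B).

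**No true difference.** Remove k non-responders selectively from Arm B, 64 per arm. The false-positive rate favouring Zevalin (nominal 2.5%) is:

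- CR 20% in both arms: 1.5% (k=0), 2.4% (k=4), 3.0% (k=6).
- CR 50% in both arms: 1.4%, 4.4%, 6.6%.

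**Single results.**

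- Borderline, all kept, 13/64 vs 24/64: |13·40 − 24·51| = 704. X² = 128·(704 − 64)² / (64·64·37·91) = 3.80, p=0.051.
- Two Arm B non-responders removed, 13/64 vs 24/62: |13·38 − 24·51| = 730. X² = 126·(730 − 63)² / (64·62·37·89) = 4.29, p=0.038.
- Typical at the design rates: 13/64 vs 30/60 gives p=0.001 and 13/64 vs 30/64 gives p=0.003, so nothing changes.

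**The case against.** The plan limits the problem in several ways.

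- The sensitivity analysis in 16.11 restores every treated violation, and 13.7 keeps those patients in follow-up, so the data will exist.
- Section 13.7 needs a severe breach of cycle-1 treatment requirements. A requested withdrawal arguably breaches nothing, so only non-compliance clearly overlaps.
- Dosing ends by day 8 or day 22, 8.1 provides for no dose modifications, Section 4.0 schedules no tumour imaging between baseline and month 6, and 18.1 requires treatment forms at end of treatment. The dosing facts should be on record before any scheduled response scan.
- The larger figures need every violation in one arm with none in CR, and no document supports that. At 20% CR in both arms, removing four Arm B non-responders leaves the false-positive rate under 2.5%.
- A positive result leads only to a recommendation for further testing.
- Objective criteria fixed before month 6 would cure the vagueness without changing the primary population.

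Much of this stands as a limit on weight. It does not close the gap. Early dosing records do not oblige anyone to classify early. The sensitivity analysis also restores ineligible patients, so it does not isolate the label, and no rule covers disagreement with the primary result. Dated, objective criteria would stop outcome-driven labelling, but they would still remove patients for an event after randomisation that treatment may cause.

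**Conclusion.** The concern holds. The deciding analysis excludes treated, randomised patients on a judgement that may follow their response, and the plan does not separate those exclusions from early stoppers who count as non-responders.

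The effect is probably small: about 1% or less with balanced stoppers not in CR, rising to 7.7% with six all in Arm B, or 11.0% at 61 per arm. These figures rest on assumed counts and, apart from the CMH check, on an unstratified test. A result near the design effect would not change; a borderline one could with two one-sided exclusions. This should be corrected because the correction is cheap, not because a large bias is expected.

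**What to change.** Amend 13.7, 16.11 and 16.21 as follows.

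- Missing, stopping or deviating from cycle-1 treatment, including withdrawal or non-compliance under 13.3.1, does not remove a patient from the primary analysis.
- Every eligible patient who received at least one dose is analysed in the randomised arm and is a non-responder unless the month-6 assessment is CR. Section 16.34 already uses eligible treated patients for adverse events.
- The set excluding major violations becomes a sensitivity analysis. It uses objective dose criteria, for example Zevalin not given or a stated number of rituximab infusions missed, applied without knowledge of the month-6 response.
- The planned all-treated sensitivity analysis stays.

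No new data, procedures or patients are needed. The reported CR rate may be slightly lower. At 20% vs 50% with 64 per arm (unstratified, corrected), power moves from 91.95% to 91.62% with three non-CR stoppers per arm, and from 91.3% to 83.5% in the worst case of six all in Arm B. With 61 per arm the same cases give 90.6% to 90.0% and 91.9% to 80.8%. That loss is the price of counting patients who did not complete treatment and did not reach CR as failures.
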